Comparative effectiveness of energy doses in critical illness

Short title: The Energy Dose Study

Principal Investigator: [name].

Protocol Version Date: 6/2/2014

NCT Number: NCT01369147

Abstract:

Protein and/or energy deficits are associated with increased rates of hospital infection, skeletal muscle weakness, impaired wound healing, and prolonged convalescence in ICU patients. To prevent or treat malnutrition, enteral nutrition (EN) and/or parenteral nutrition (PN) are routinely given worldwide to a significant proportion of ICU patients. Optimal caloric requirements in critically ill patients are unknown due to a lack of rigorous randomized clinical trials. The comparative efficacy of energy doses in critically ill patients is unknown and clinical recommendations are conflicting and controversial; this issue is the focus of our study.

We have designed this pilot, single-center Randomized Clinical Trial (RCT) to prospectively compare, for the first time, the clinical efficacy of different energy doses in ICU patients requiring PN due to intestinal failure/dysfunction. A total of 60 patients will be studied (20 per energy dose group) to generate critical preliminary data needed to inform subsequent appropriately powered Phase III multicenter trials.

The primary aim of this study is to perform a controlled, double-blind, prospective, randomized, intent-to-treat Phase II clinical trial to test the efficacy of three specific energy doses [0.6, 1.0 and 1.3 x measured REE (resting energy expenditure), respectively], given for 28 consecutive days during the ICU course, on 28-day total hospital-acquired infections (primary endpoint), Blood Stream Infections (BSI), and other important clinical outcomes in medical/surgical ICU patients requiring specialized parenteral \pm enteral feeding. We would also determine, in these subjects A) the impact of cumulative and mean daily 28-day energy deficits [energy intake-measured REE] on clinical outcome endpoints; and B) the practical utility of estimated REE determined by Harris-Benedict equation versus measured REE across different energy doses. We would also like to determine the impact of administered energy dose and energy deficits on global metabolomic patterns over time and their association with key clinical outcomes.

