Exclusion criteria: 1) The patient is pregnant; 2) The patient has unresuscitated clinical sepsis [defined as unstable blood pressure despite vasopressor support and mean arterial pressure (MAP) < 60 mm Hg on at least 3 consecutive readings within a 3-hour period during the 24 hours prior to study entry; 3); 3) The patient was admitted to the ICU following trauma or burns; 4) The patient has significant renal dysfunction (defined as serum creatinine > 2.5 mg/dL or deemed to have significant acute kidney injury by the primary physicians) and is not receiving continuous renal replacement therapy (CRRT) or intermittent hemodialysis; 5) The patient has previously undergone an organ transplantation; 6) the patient has a current malignancy or is currently receiving an active regimen of chemotherapy and/or radiotherapy to treat a previously diagnosed malignancy[#]; 7) the patient has a history of HIV/AIDS; 8) The patient has received any investigational drug within 60 days prior to study entry; and 9) The patient is unable or unwilling to participate in study procedures such as longitudinal blood draws and administration of study nutrient formulations.

[#] [†] Patients with malignant metastasis and terminal untreatable carcinoma will be excluded.

If the patient meets criteria, we will consent the patient's legally authorized representative (LAR), as potential study subjects will be mechanically ventilated and probably sedated.

Randomization of study subjects: A research team member will calculate the APACHE II score. Treatment assignments will be stratified according to clinical center and on the basis of illness severity (APACHE II score, either ≤ 15 or > 15). The treatment assignments will be generated by the Emory-based DCC with the use of a pseudo-random-number generator with randomly permuted blocks that will be used to ensure balance between the numbers of subjects assigned to the REE x 0.6, 1.0 or 1.3 groups, respectively.

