standardized CRFs. The primary endpoint is total nosocomial infection rate during the 28-day study period. Secondary Aim 1 post-entry endpoints to be monitored include: 1) 28-day hospital mortality; 2) Rate of new nosocomial blood stream infections (BSIs) during the initial 28 days; 3) Rate of new nosocomial infections during the initial 28 days; 4) mean ICU SOFA score; 5) ICU ventilator-free days at day 28; 6) ICU and total hospital length of stay.

Hospital nutrition support - Administration of double blind parenteral and enteral nutrition:

Briefly, the nutritional goals are to provide total daily calorie (kcal) intake [from PN + dextrose-containing IV fluids (> 500 mL/day) + propofol/clevidipine + any enteral feedings) at 0.6, 1.0 or 1.3 x baseline MEE (per metabolic cart). We will then serially adjust total PN/EN energy dosing based on real-time serial cart REE measurements during the ICU stay, as indicated by the energy dose group to which the patient is randomized. The total amino acid/protein intake goal is 1.2 g/kg/day. Dextrose will initially comprise 70% of PN non-amino acid kcal and IV fat (30% Intralipid[®]) 30% of PN non-amino acid kcal daily, adjusted as clinically indicated. The 1.0 x REE energy dose study group will serve as the control group in this CER study. Study PN will be continued only if deemed indicated by the investigators and the primary physicians. Daily intake of study PN volume (mL), PN dextrose (g), PN lipid emulsion (g), intake of study tube feeding volume, and daily PN and enteral (oral or tube feeding) volumes will be calculated and entered into the CRFs daily for the initial 28 days after entry, beginning on day 1.

Study subjects will receive a maximum of 28 days of double blind study PN ± EN. Subjects will be transitioned from PN to enteral feeds as soon as tolerated and clinically indicated. Study PN will be discontinued when enteral intake of \geq 50% of energy requirements is achieved for \geq 48 hr. The amount of PN administered will be decreased as a function of actual enteral nutrient intake to maintain daily goals. The 24-hr daily study PN will be prepared under sterile laminar air flow hood conditions by the unblinded research pharmacist and pharmacy technician at each site. The study EN will be made in the Metabolic Kitchen or in the compounding area of the pharmacy.

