Data and Safety Monitoring Board (DSMB): The Data and Safety Monitoring Board (DSMB) will act in an advisory capacity to the National Institute of Diabetes, Digestive and Kidney Diseases (NIDDK) to monitor subject safety and evaluate the efficacy of the intervention being studied in this clinical trial funded by the NIDDK. The DSMB will be appointed by the PIs upon study funding, and approved by NIDDK program staff. The DSMB will be composed of at least two experienced clinical nutrition support investigators not otherwise participating in the study and not affiliated with Emory. A biostatistician not otherwise participating in the study will also be named to the DSMB. The DSMB will meet twice yearly, and as needed, and will receive blinded and unblinded reports on study progress prepared by the DCC.

Statistical Analysis:

Continuous variables will be summarized with standard descriptive statistics and represented graphically with displays such as scatterplots, box plots, line plots and histograms, while categorical variables (adverse events) will be described by frequency tables.

For Aim 1: The primary analyses of the data will be performed according to subjects' original treatment assignment (i.e., intention-to-treat analyses) and the inclusion of all data from all subjects randomized in the final analysis. Rates of infection (i.e., BSI and total nosocomial infections) per 1000 hospital days will be estimated overall and for each of the 3 energy doses. Confidence intervals (95%) for the incidence rates will be estimated using an exact method based on the Poisson distribution.

Additionally incidence rates of infection will be estimated by performing a generalized estimating equations (GEE) Poisson regression analysis of the counts, implemented using SAS Proc Genmod, using an exchangeable correlation structure for the repeated counts within subject. The incidence rate ratio (IRR) is the ratio of the incidence density in one group to that of another group. Results by each baseline covariate will be presented as the IRR and the 95% confidence interval (CI). This GEE model can also accommodate time-dependent covariates such as daily blood glucose levels measured before an infection and total 28-day energy (cumulative deficit or as a time-dependent covariate).

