Twenty-eight day mortality will be summarized as a proportion plus the 95% confidence interval (overall and for each treatment group). The 28-day mortality will be compared between treatment groups using a chi-square or Fisher's exact test. The potential association of each of the categorical prognostic factors (gender, race, high or low Apache score, clinical center) with mortality will also be evaluated using a Chi-square test or Fisher's exact test. Baseline continuous prognostic factors (age, SOFA score, blood glucose) will be compared by treatment group using the Wilcoxon rank-sum test. Odds ratios will be calculated to measure the degree of association. All statistical tests will be 2-sided. Factors significant to at least a value of $P \leq 0.20$ in the univariable analyses will be used in multivariable logistic regression analyses. Forward and backward stepwise selection will be used if necessary to choose prognostic variables for a multivariable logistic regression model. The odds ratio and its 95% confidence interval will be calculated for each factor in the presence of others in the final model.

Days on mechanical ventilation, length of ICU stay and hospital length of stay will be summarized with percentiles (25th, 50th and 75th) and the median absolute deviation. These secondary outcomes will be compared between the 3 treatment groups using the Kruskal-Wallis test. Repeated-measures analyses of daily SOFA scores and laboratory measures such as blood glucose will be analyzed with a means model with SAS Proc Mixed (version 9, mixed linear models) providing separate estimates of the means by time on study (days 0, 3, 7, 14, 21, and 28) and treatment group (energy dose: 0.6, 1.0 and 1.3 x REE). An unstructured variance-covariance form among the repeated measurements will be assumed for each outcome and estimates of the standard errors of parameters will be used to perform statistical tests and construct 95% confidence intervals. T-tests will be used to compare the pairwise differences between the model-based treatment means (least-squares means) at each time point. Statistical tests will be 2-sided. The model-based means are unbiased with unbalanced and missing data, so long as the missing data are non-informative (missing at random). A dropout process is assumed to be missing at random if; conditional on the observed data, the dropout is independent of the unobserved measurements.

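### Allocation is stratified by center and APACHE II, but no arm comparison is prespecified to use those strata; the cost is lost power, mainly in the secondary tests

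*Combined protocol and SAP*

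**What the plan says.** Randomization of study subjects: "Treatment assignments will be stratified according to clinical center and on the basis of illness severity", with APACHE II cut at 15, "with randomly permuted blocks that will be used to ensure balance between the numbers of subjects" in the three arms. Block size is not given. Study Procedures names two hospitals, so there are four strata.

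Serial data entry: "The primary endpoint is total nosocomial infection rate during the 28-day study period".

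Statistical Analysis, For Aim 1, on infections: rates per 1000 hospital days overall and by arm, where "Confidence intervals (95%) for the incidence rates will be estimated using an exact method based on the Poisson distribution". Then: "Additionally incidence rates of infection will be estimated by performing a generalized estimating equations (GEE) Poisson regression analysis of the counts". The plan promises a rate ratio for each baseline covariate but does not list the covariates or say that the arm ratio is adjusted for them. It adds: "This GEE model can also accommodate time-dependent covariates such as daily blood glucose levels measured before an infection", and names energy deficit as another such covariate.

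The same section, on secondary outcomes: mortality across arms by chi-square or Fisher's exact test. For ventilation days and ICU and hospital stay, "These secondary outcomes will be compared between the 3 treatment groups using the Kruskal-Wallis test". SOFA and glucose get a mixed model with time and treatment means only. APACHE category and center are listed as prognostic factors for mortality. They reach the multivariable logistic model only through a univariable screen at P of 0.20 or less, with stepwise selection if needed. Arm is not stated to be a forced term.

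**The concern.** Stratified blocks make the arms alike on center and APACHE II, so differences between strata contribute little to chance differences between arms. An analysis that ignores the strata still counts that variation as noise. Its null distribution is then too wide, the test rejects less often than its nominal level, and power is lost. The plan itself treats both factors as prognostic for mortality, so it expects them to matter.

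Leaving adjustment unstated also leaves it open to choice after the data are seen. The infection model is where this discretion counts: the exact Poisson intervals describe each arm separately, so the regression supplies the only between-arm infection measure described, while the Hypothesis section compares 1.3 x REE with the lower doses.

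**Working it through.** **Inputs from the documents.** 60 patients, 20 per arm (3 x 20 = 60); four strata; permuted blocks; two-sided tests. There is no power calculation to reproduce, and no alpha, infection rate, mortality, stay distribution or stratum effect is given.

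**Assumptions.** Alpha 0.05; blocks of 3 or 6; half the patients above APACHE 15; 40% at one hospital; SD of log stay 0.6.

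**Step 1: size of the unstratified secondary tests.** Let s be the share of outcome variance lying between strata. With balanced strata the three-arm statistic behaves roughly as (1 − s) times a chi-square on 2 df. Since P(chi-square on 2 df > x) = exp(−x/2), the true size of a nominal 0.05 test is about 0.05^(1/(1 − s)).

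- Stay, APACHE shift d on the log scale, half the patients in each class: between-stratum variance = d²/4.
  - d = 0.4: s = 0.04/(0.36 + 0.04) = 0.100; size = 0.05^(1/0.900) = 0.036.
  - d = 0.8: s = 0.16/(0.36 + 0.16) = 0.308; size = 0.05^(1/0.692) = 0.013.
  - Simulated Kruskal-Wallis: 0.035 and 0.013 (a separate run of 4,000 trials per setting: 0.037 and 0.012; with no shift, 0.055).
- Mortality by APACHE class:
  - 10% and 30%: s = 0.10²/(0.20 x 0.80) = 0.0625; size = 0.041. Simulated chi-square: 0.044.
  - 10% and 50%: s = 0.20²/(0.30 x 0.70) = 0.190; size = 0.025. Simulated: 0.028.
  - 20% and 20%: s = 0; size = 0.05. Simulated: 0.053.

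**Step 2: power recovered by stratified tests** (simulation; one arm shifted 0.5 on log stay, or by 1.5 in log odds of death).

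| Outcome | Stratum effect | Unstratified | Stratified |
|---|---|---|---|
| Stay | none | 0.73 | 0.70 |
| Stay | shift 0.4 | 0.69 | 0.72 |
| Stay | shift 0.8 | 0.53 | 0.70 |
| Death | 20% / 20% | 0.64 | 0.64 |
| Death | 10% / 30% | 0.54 | 0.58 |
| Death | 10% / 50% | 0.40 | 0.51 |

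A separate run of the two shifted stay rows gave 0.67 to 0.70 and 0.52 to 0.70. The stratified rank test held its size (0.044 to 0.053).

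**Step 3: infection rate ratio.** Poisson regression on one count per patient, log-days offset, uncorrected robust standard error (a simplification of the planned model), no treatment effect, 1,500 trials per setting, center rate ratio 1.5 (1 in the first row). SD is the actual spread of the log rate ratio, 1.3 against 1.0 x REE; SE is the mean reported standard error. Each pair is unadjusted then adjusted.

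| APACHE rate ratio, base mean, dispersion | SD | SE | Type I error |
|---|---|---|---|
| 1, 1.0, 0.5 | 0.400, 0.401 | 0.383, 0.377 | 0.059, 0.065 |
| 2, 1.0, 0.5 | 0.401, 0.402 | 0.387, 0.359 | 0.058, 0.075 |
| 3, 0.6, 0.5 | 0.509, 0.500 | 0.479, 0.439 | 0.064, 0.086 |
| 3, 1.0, 0 | 0.308, 0.304 | 0.338, 0.282 | 0.025, 0.071 |

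The largest fall in SD here is (0.509 − 0.500)/0.509 = 1.8%. The reported SE falls much more, but in the second row it goes from 0.387/0.401 = 0.97 of the true SD to 0.359/0.402 = 0.89. Over all 16 settings type I error was 0.045 to 0.068 unadjusted, apart from the 0.025 in the last row, and 0.059 to 0.086 adjusted. In a further simulation, a leverage-corrected standard error with a t reference brought the adjusted model to 0.046 to 0.047.

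**The case against.** The case for leaving the plan alone has four parts.

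- **The trial is a 60-patient pilot with no power target, and the omission does not threaten validity.** This stands. It limits the weight of the point, not its truth.
- **The plan is silent on adjustment; it does not rule it out.** It mentions baseline covariates for the infection model, and the mortality model can take both strata. A strongly prognostic stratum is also the one most likely to pass the screen. This stands in part: the gap is that adjustment is unspecified. It does not reach the mortality arm test or Kruskal-Wallis, which are unstratified as written.
- **The strata may not matter.** The hospitals share ICU guidelines and catheter procedures (Clinical management guidelines; Protections Against Risk), so a center effect is not evident. Fair, but the plan calls both factors prognostic, and Step 2 shows a small cost if they are not.
- **Adjusting the infection model as it stands makes error control worse.** This stands, and is why the fix includes a small-sample correction.

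A reader might infer from the omission that the infection intervals are materially too wide. Step 3 does not support that: in most settings the unadjusted robust standard error is already slightly below the true SD, because small-sample bias offsets the ignored strata. A reader might also infer that the arm rate ratio will be adjusted for glucose or energy deficit, which the randomised dose drives. The text says only that the model can take such covariates, and Aim 2 gives energy deficit a separate purpose.

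**Conclusion.** The point holds as a gap in prespecification with a conservative consequence. Allocation uses center and APACHE II; no arm comparison is stated to use them, and in the mortality model they can be dropped by the screen or by stepwise selection.

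The material loss is in the secondary tests and depends on how prognostic APACHE is: for stays, about 3 points of power at a log shift of 0.4 and 17 at 0.8 (0.70 − 0.53); for mortality, 4 points at 10% against 30% and 11 at 10% against 50%. For the infection rate ratio the true gain from adjustment is about 1%, under 2% throughout. All of these figures rest on assumed values.

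It would be wrong to read this as a source of false positives. The unadjusted infection model's type I error, up to 0.068, reflects the uncorrected robust standard error at this sample size: it was 0.055 to 0.059 even when the strata had no effect.

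**What to change.** In Statistical Analysis, For Aim 1:

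1. **Ventilation days and stays:** replace Kruskal-Wallis with a stratified rank test (van Elteren type, extended to three arms).
2. **Mortality:** use a Cochran-Mantel-Haenszel test across arms, stratified by center and APACHE class. Keep arm, center and APACHE class in the logistic model outside the P ≤ 0.20 screen and any stepwise step. At an assumed 20% mortality there would be 60 x 0.20 = 12 deaths for four such parameters, so the stratified test should carry the arm comparison.
3. **Infections:** state that the arm rate ratio comes from a Poisson model with arm, center and APACHE class as fixed terms and log at-risk days as offset, using a small-sample-corrected robust standard error with a t reference.
4. **Post-randomisation covariates:** state that models containing glucose or energy deficit are separate, exploratory Aim 2 analyses and not the source of the arm rate ratio.

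The cost is wording only: both factors are already collected, and the infection model gains two parameters. The statistical downside is about 2 to 3 points of power if the strata turn out not to be prognostic.

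### With 20 patients per arm, the infection rate ratios rest on a GEE with no stated standard error, small-sample correction or zero-event rule: total-infection intervals are likely modestly too narrow at moderate rates, and BSI ratios involving an empty arm cannot be estimated

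*Combined protocol and SAP*

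**What the plan says.** The Abstract sets the size: "A total of 60 patients will be studied (20 per energy dose group"), as a pilot to "generate critical preliminary data needed to inform subsequent appropriately powered Phase III multicenter trials". Under Study Procedures (serial data entry) the main outcome is defined: "The primary endpoint is total nosocomial infection rate during the 28-day study period". A secondary outcome there is "Rate of new nosocomial blood stream infections (BSIs) during the initial 28 days".

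Statistical Analysis, For Aim 1, then gives two layers for infections:

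- Rates for BSI and for total infections, "per 1000 hospital days will be estimated overall and for each of the 3 energy doses". For these, "Confidence intervals (95%) for the incidence rates will be estimated using an exact method based on the Poisson distribution".
- In addition, a Poisson GEE on the counts, "implemented using SAS Proc Genmod, using an exchangeable correlation structure for the repeated counts within subject". "Results by each baseline covariate will be presented as the IRR and the 95% confidence interval (CI").

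The second layer is the only method named for comparing infections between doses. It does not say whether the standard errors are empirical or model-based, gives no small-sample adjustment or t reference, and does not say what happens if an arm has no event. For mortality, the same section offers Fisher's exact test. No infection rate, between-patient variation or expected event count appears anywhere.

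**The concern.** GEE inference is justified by a large number of independent units. Here the unit is the patient, and each arm has 20. The uncorrected empirical (sandwich) variance tends to be too small with so few units, more so when a few patients contribute most of the infections. Normal quantiles add a little to the shortfall. An IRR interval that is too narrow overstates what the pilot has learned about dose, and that interval is what a Phase III design team would carry forward.

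The second problem is sparse BSI data. A log-linear model has no finite IRR when one of the two arms compared has no event. The plan protects single-arm rates and mortality against small numbers by exact methods, but not the infection ratios.

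**Working it through.** **The plan's own figure.** 3 arms x 20 = 60. With no power, effect size or infection rate stated, there is nothing further to reproduce.

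**Inputs.** From the documents: 20 per arm, 28 days, Poisson GEE, 95% intervals. Assumed, because the documents do not give them: hospital days uniform on 7 to 28 (mean 17.5, so 20 x 17.5 = 350 days per arm); 0.5 to 1.5 infections per patient (0.5/17.5 to 1.5/17.5, about 29 to 86 per 1000 days); gamma variation in infection risk between patients with variance 0, 1 or 2; no true dose effect.

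**Formulae.** With y the count and t the days of a patient, the arm rate is r = Σy/Σt. The log IRR is the difference of two log rates. The plain empirical variance of one log rate is Σ(y − rt)²/(Σy)². The Mancl-DeRouen correction divides each residual by 1 − h, with h = t/Σt.

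**Total infections, by infections per patient.** 40,000 simulated two-arm data sets per setting, for means of 0.5, 0.75, 1.0 and 1.5:

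| Between-patient variance | Two-sided error, plain SE and z | Coverage (100 minus error) |
|---|---|---|
| 0 | 5.6 to 6.3% | 93.7 to 94.4% |
| 1 | 6.9 to 8.2% | 91.8 to 93.1% |
| 2 | 7.8 to 9.2% | 90.8 to 92.2% |

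Standard errors were 5 to 14% too small. With the correction and t(38), error over the same settings was 3.6 to 6.6%. Repeat runs agreed to within about half a point.

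**Total infections, by rate.** Coverage of the plain interval:

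| Rate per 1000 days | Events per arm | Variance 0 | 0.5 | 1 | 2 |
|---|---|---|---|---|---|
| 15 | about 5 | 96.9% | 96.5% | 96.1% | 95.6% |
| 25 | 8.8 | 94.8% | 94.2% | 93.7% | 92.8% |
| 40 | 14 | 94.3% | 93.4% | 92.8% | 91.4% |
| 60 | 21 | 93.8% | 92.9% | 92.4% | 90.9% |

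At 25 to 60 per 1000 the corrected interval covers 93.6 to 96.9%. A full three-arm exchangeable GEE on weekly counts (500 trials per setting) gave 91 to 95% for the plain interval at 25 to 40 per 1000, with simulation error of about 1 point. At 0.25 infections per patient (20 x 0.25 = 5 events per arm) the plain interval's error was 2.9 to 4.1%, so the direction reverses.

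**Price of the correction.** Average h is 1/20, so the standard error grows by about 1/0.95 = 1.053. The quantile ratio is 2.024/1.960 = 1.033. The product is 1.09, a little more with unequal stays. In the simulation at 40 per 1000 and variance 1, the median margin factor went from x2.56 to x2.81: ln 2.81 / ln 2.56 = 1.033/0.940 = 1.10.

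**BSI, chance of at least one empty arm.** If a proportion p of patients has a BSI, one arm is empty with probability (1 − p)^20, and at least one of three with 1 − [1 − (1 − p)^20]³:

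| p | One given arm empty | At least one of three |
|---|---|---|
| 10% | 0.9^20 = 0.122 | 1 − 0.878³ = 32% |
| 15% | 0.85^20 = 0.039 | 1 − 0.961³ = 11% |
| 20% | 0.8^20 = 0.012 | 1 − 0.988³ = 3% |

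On the rate scale at 350 days per arm, using exp(−rate x days) and its gamma-mixed version (variance up to 2), the chance is 87 to 88% at 2 per 1000 days, 44 to 49% at 5, and 9 to 14% at 10. If every patient stayed 28 days (560 days per arm), it is 69 to 72%, 17 to 23% and 1 to 4%. When a BSI ratio can be estimated, its plain interval is very wide and covers 98% or more.

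**The case against.** Five points can be made for the plan, and each limits the concern.

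- *A reader might infer that the total-infection intervals are simply too narrow.* The documents do not support that. The shortfall depends on a rate and a dispersion they do not state, and at about 5 events per arm the intervals over-cover.
- *A reader might infer that the plan specifies robust standard errors.* It does not. The empirical form is the usual Genmod GEE output, but the choice is left open. This does not rescue the plan: intervals from a Poisson variance that ignores clustering did worse, covering 73 to 87% at 40 to 60 per 1000 days with variance 1 to 2.
- *A reader might infer that a false dose effect will be declared too often.* For infections the section specifies rates, ratios and intervals, with no P value or alpha. The sentence on two-sided tests sits in the mortality paragraph. The consequence is for interval reporting in a pilot. Inference still matters, because Hypothesis 1 and Specific Aim 1 are about comparative efficacy on infections.
- *A reader might infer that the BSI analysis can return nothing.* It cannot. Exact Poisson intervals for each arm exist with zero events, and a ratio between two arms that both have events is still estimable. Only ratios involving the empty arm fail.
- *Exact or mid-P ratio intervals assume unclustered events.* This stands. At 0.2 events per patient, mid-P error was 3.8%, 5.8% and 7.8% for variance 0, 1 and 2; the effect is small when BSI is rarer.

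**Conclusion.** The concern holds in a limited form. The one between-dose infection analysis is a large-sample method applied to 20 patients per arm, with the standard error, any small-sample adjustment and the empty-arm case all unstated.

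For total infections, the usual uncorrected interval is likely modestly too narrow at moderate rates: about 91 to 94% coverage at 0.5 to 1.5 infections per patient, and conservative at about 5 or fewer events per arm. For BSI the gap is one of estimability, not narrowness. Its chance runs from 3% to 32% on the patient-proportion assumptions, and is higher at low rates per hospital day.

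All these figures rest on assumed rates, stays and dispersion. The absence of the three specifications does not. The matter is worth correcting before the data are analysed, but it does not undermine the pilot.

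**What to change.** In Statistical Analysis, For Aim 1:

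1. State that IRR intervals use the empirical standard error with a bias correction (Mancl-DeRouen or equivalent) and t quantiles, with the degrees of freedom named.
2. State that when an arm has no BSI, ratios involving it are reported with an exact conditional, mid-P or penalised (Firth-type) interval. Choose one in advance, and note that exact and mid-P limits assume events do not cluster within patients.
3. If a dose P value for infections is wanted, a permutation test that respects the hospital by APACHE II strata and the permuted blocks is an option. It is not required, and it may disagree with the model-based interval.

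The cost is a few sentences and some programming, with no extra patients or data. Total-infection IRR intervals become about 10% wider on the log scale, including at low event counts, where the plain interval is already conservative. The bias correction does not help an empty BSI arm, so items 1 and 2 are both needed.

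### The infection GEE's exchangeable working correlation need not return the incidence density by which the plan defines its IRR, and it is not guaranteed consistent for the time-dependent covariates

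*Combined protocol and SAP*

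**What the plan says.** All of this is in the protocol's Statistical Analysis section, under Aim 1.

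- **Direct rates.** "Rates of infection (i.e., BSI and total nosocomial infections) per 1000 hospital days will be estimated overall and for each of the 3 energy doses". Their intervals come from an exact Poisson method.
- **The model.** "Additionally incidence rates of infection will be estimated by performing a generalized estimating equations (GEE) Poisson regression analysis of the counts", "using an exchangeable correlation structure for the repeated counts within subject".
- **The estimand.** "The incidence rate ratio (IRR) is the ratio of the incidence density in one group to that of another group".
- **Extensions.** "This GEE model can also accommodate time-dependent covariates such as daily blood glucose levels measured before an infection". Energy deficit is named as a further covariate, either cumulative or varying over time.

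The plan does not state the record unit (day, week or patient), an offset for days at risk, the variance estimator, or a sensitivity analysis under another working correlation. Repeated counts within a subject and daily covariates both imply several records per patient.

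Hospital stay, the denominator of the rate, is itself a secondary endpoint compared between the three arms.

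**The concern.** An incidence density gives every patient-day equal weight. An exchangeable GEE does not: with positive ρ, a day from a long-stay patient counts for less than a day from a short-stay patient. If long-stay patients are also those with more infections, the model and the direct calculation estimate different quantities, yet the plan calls both the infection rate.

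The same paragraph invites time-dependent covariates. With a non-diagonal working correlation, GEE is consistent in general only if a day's expected count, given that day's covariate, does not depend on the covariate on other days. That is doubtful if infection affects later glucose or energy balance.

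The GEE is the only model described that gives an infection IRR. The trial is a pilot meant to inform Phase III design, so a published rate or ratio that does not match its own definition would carry forward.

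**Working it through.** The plan gives no infection rate, IRR or correlation to reproduce. It supplies only 20 patients per arm, 28 days, and rates per 1000 hospital days. **All other inputs below are assumptions.**

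**1. Formula.** For a dose-only Poisson GEE on patient-day records, the arm rate is

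rate = Σ wᵢyᵢ / Σ wᵢnᵢ, with wᵢ = 1/(1+(nᵢ−1)ρ),

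where yᵢ is the patient's infections and nᵢ the days. At ρ = 0 this is events/days. In one simulated data set, a GEE routine and this formula agreed under exchangeable (27.68 per 1000 days, ρ = 0.119, IRR 0.994). Independence on patient-days gave 40.30 and IRR 0.891. So did one record per patient with a log(days) offset.

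**2. Worked arm of 20.** Take 12 uninfected patients with 10 days each and 8 infected patients with 25 days each and 14 infections in all.

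- Direct: 14/(120+200) = 43.8 per 1000 days.
- ρ = 0.02: weights 1/1.18 = 0.847 and 1/1.48 = 0.676; 0.676×14/(0.847×120 + 0.676×200) = 39.9.
- ρ = 0.05: weights 1/1.45 = 0.690 and 1/2.20 = 0.4545; 0.4545×14/(0.690×120 + 0.4545×200) = 36.6.

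But ρ is estimated, not chosen. If six infected patients have 2 infections and two have 1, the fitted ρ is −0.029 and the GEE rate is 56.2, above the direct rate. The split 3,3,2,2,1,1,1,1 gives ρ = −0.010 and 46.8. For these data ρ reaches 0.02 only if one patient has at least 5 infections or two have at least 4.

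**3. Large-sample rates and IRRs.** Assumed: daily hazard 0.02–0.03, base stay about 12 days, cap 28 days, gamma frailty for patient heterogeneity.

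| Setting | First-arm rate, density v exchangeable | IRR, density v exchangeable |
|---|---|---|
| No frailty, +7 days per infection | 30.1 v 30.0 | 0.671 v 0.670 |
| Frailty variance 1, no prolongation | 30.0 v 30.0 | 0.664 v 0.664 |
| Variance 1, +7 days in both arms | 35.1 v 28.0 (−20%) | 0.648 v 0.643 |
| Variance 2, +10 days in both arms | 39.5 v 27.7 (−30%) | 0.645 v 0.629 |
| Variance 1, +10 v +3 days, same hazard | 35.7 v 27.5 | 0.935 v 1.039 |
| Variance 2, +10 v +3 days, same hazard | 39.7 v 27.1 | 0.916 v 1.031 |

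A difference in base stay alone also moves the IRR. With equal hazard, +7 days in both arms and base stay of 14 v 9 days, it was 1.065 v 0.969 (variance 1) and 1.111 v 0.955 (variance 2).

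**4. At 20 per arm** (3,000 runs in each of three settings with frailty).

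- Mean first-arm rates: 34.5 v 30.2, 34.9 v 29.9 and 38.5 v 29.0.
- Mean absolute shift in log IRR: 0.05 to 0.12, against an SD of log IRR of 0.68 to 0.81.
- SD of log IRR, independence v exchangeable: 0.75 v 0.75, 0.68 v 0.68 and 0.81 v 0.80.
- Estimated ρ was negative in 6–21% of runs.

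**5. Time-dependent covariate.** IRR per SD of glucose, independence v exchangeable, with a simulated within-patient value of 1.30; feedback means glucose rises 1.5 SD the day after infection.

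- No feedback, frailty variance 1: 1.28 v 1.30.
- Feedback, no frailty: 1.31 v 1.31.
- Feedback, frailty variance 1: 1.56 v 1.35.
- Feedback, frailty variance 2: 1.74 v 1.35.

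With both feedback and heterogeneity, the coefficient depends on the working correlation.

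**The case against.** **The direct rates are untouched.** The plan first gives events per 1000 hospital days with exact Poisson intervals and adds the GEE afterwards. This stands: a reader can form the density ratio by dividing two direct rates. But the planned IRRs with confidence intervals come from the GEE.

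**The record unit is not stated.** With one record per patient and a log-days offset, the issue disappears. True, but then there would be no within-subject correlation to specify and no place for daily covariates, so the text points the other way.

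**The GEE rate is not always lower.** A reader might infer that longer stay in infected patients forces it down. The working shows otherwise: non-zero ρ is also needed, and in small samples ρ can be negative and the gap reversed. The documents do not state that infection prolongs stay in this trial.

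**The IRR hardly matters at this size.** When stay patterns match across arms the shift is negligible. When they differ it is still well inside sampling error. This stands and limits the weight of the point. The plan does, however, compare stay between arms, so a difference cannot be ruled out.

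**The covariate problem is conditional, and independence is no cure for causality.** The plan says only that the model can take such covariates, and limits glucose to levels before an infection. Glucose targets and adjustment of parenteral nutrition to enteral intake may dampen feedback. Against that, a level taken before a second infection may follow a first. The weekly mean measured energy expenditure is also applied to all seven days, so measurements after an infection can enter the deficit on earlier days. The objection that independence can lie further from a within-patient effect (1.56–1.74 v 1.30) is correct.

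**Conclusion.** The mismatch is real but conditional. The plan defines one quantity and names an estimator that need not return it when the estimated ρ is non-zero and stay is related to infection.

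- **Rate:** about 20–30% below the density in large samples, assuming patient heterogeneity and 7–10 extra days per infection; no large-sample gap without heterogeneity or without prolongation; either direction in a small sample.
- **Dose IRR:** nearly unchanged when stay patterns match; roughly 10% or more when they differ (for example 1.039/0.935 = 1.11 and 0.955/1.111 = 0.86). At 20 per arm this is small against an SD of log IRR near 0.7.
- **Time-dependent covariates:** exchangeable is not guaranteed consistent for the marginal association if earlier infection affects later values.

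A reader might infer that the primary result is invalid, or that the glucose and deficit coefficients are certain to be wrong. The documents support neither: the direct rates stand, and the size of any feedback is unknown. The change is worth making because it is cheap and makes the estimate match its definition.

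**What to change.** In the Aim 1 analysis:

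1. State the record unit and days at risk. For the dose and baseline-covariate IRRs, use patient-day records with an independence working correlation (TYPE=IND in Proc Genmod) or, equivalently, one record per patient with a log days-at-risk offset.
2. Use robust standard errors clustered on patient, preferably with a small-sample correction given 60 patients.
3. Keep exchangeable as a sensitivity analysis.
4. For models with time-dependent covariates, state the target. If it is the marginal association, use independence and report the coefficients as associations, not causal effects.

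The dose-only GEE rates then equal the direct events/days rates.

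**Cost:** one option in the code and a few words in the plan. No loss of precision was seen in the simulated settings. The downside is one of interpretation: the independence IRR is a person-time-weighted density ratio and may lie further from a within-patient or hazard effect, so the report should say which it presents.
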